1.2. Rationale for the study

Because the infectious aetiology of AECOPD has been suggested to vary according to geographical region, the primary purpose of this study (which will be conducted in several countries in Asia Pacific) is to evaluate the occurrence of potential bacterial and viral pathogens in the sputum of stable COPD patients and at the time of AECOPD. Given the increasing and projected burden of COPD in the Asia Pacific region, this study will also evaluate the frequency, severity and duration of AECOPD, as well as the impact of AECOPD on health-related quality of life (HRQOL), healthcare utilisation and lung function.

In addition, both PCR and bacteriological methods will be used for characterisation and (quantification in some cases) of bacteria in sputum. To date, identification of bacteria and assessment of bacterial load is done in the vast majority of cases by culture. However, the few studies that have compared culture with PCR demonstrated that PCR is more discriminatory at detecting typical airway bacteria [Curran, 2007; Singh, 2014]. Moreover, in a multi-centre study, PCR has the advantage that it can be performed on stored sputum samples, and can therefore be done centrally, whereas culture has to be performed on fresh sputum samples, which can lead to variable results due to variability in testing methods between laboratories.

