9.2. Determination of sample size

The primary objective of this study is to describe the proportion of bacterial and viral pathogens (overall and by species) detected in sputum in stable COPD and during AECOPD.

Assuming around 90% of the All Enrolled Set participated in the study, on average 1 AECOPD visit and 80% of the above population set can provide an evaluable sputum sample at AECOPD, for 240, 200, 160, and 50 enrolled subjects, one may expect around 180, 140, 120, 40 sputum samples, respectively. Assuming that results from these sputum samples are independent and that the between country variability is much smaller than the within country variability, we would have the following 95% exact confidence interval for different incidences in sputum samples from exacerbations (see [Table 12](#)).

Table 12 Exact 95% confidence intervals of the percentage of occurrence of a specific bacterium from sputum collected during AECOPD

%	Number of evaluable sputum samples during AECOPD			
	N=180	N=140	N=120	N=40
5	[2.3 ; 9.3]	[2.0 ; 10.0]	[1.9 ; 10.6]	[0.6 ; 16.9]
10	[6.0 ; 15.3]	[5.6 ; 16.2]	[5.3 ; 16.8]	[2.8 ; 23.7]
20	[14.4 ; 26.6]	[13.7 ; 27.6]	[13.3 ; 28.3]	[9.1 ; 35.6]
30	[23.4 ; 37.3]	[22.6 ; 38.3]	[22.0 ; 39.0]	[16.6 ; 46.5]
40	[32.8 ; 47.6]	[31.8 ; 48.6]	[31.2 ; 49.3]	[24.9 ; 56.7]
50	[42.5 ; 57.5]	[41.4 ; 58.6]	[40.7 ; 59.3]	[33.8 ; 66.2]

N = total number of evaluable sputum samples during AECOPD.

One of the secondary objectives is to estimate the incidence rate of all-cause AECOPDs in the study population.

Assuming around 80% of the all enrolled set completed the study, for 240, 200, 160 and 50 subjects enrolled, one would have at least 190, 160, 130 and 40 subjects evaluable respectively. Assuming further that around 80% of the subjects can provide an evaluable sputum sample at AECOPD, this would lead to around 150, 130, 100, 30 subjects (see [Table 13](#)).

Table 13 95% confidence intervals of AECOPD incidence rates with different overdispersion values

			$\Phi = 1$		$\Phi = 1.5$		$\Phi = 2$	
0.2 AECOPD/ subject/ year			95% CI*		95% CI*		95% CI*	
T	n	Value (n/T)	LL	UL	LL	UL	LL	UL
30	6	0.20	0.04	0.36	0.00	0.40	-0.03	0.43
100	20	0.20	0.11	0.29	0.09	0.31	0.08	0.32
130	26	0.20	0.12	0.28	0.11	0.29	0.09	0.31
150	30	0.20	0.13	0.27	0.11	0.29	0.10	0.30
1 AECOPD/ subject/ year			95% CI*		95% CI*		95% CI*	
T	n	Value (n/T)	LL	UL	LL	UL	LL	UL
40	40	1.00	0.69	1.31	0.62	1.38	0.56	1.44
130	130	1.00	0.83	1.17	0.79	1.21	0.76	1.24

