6.3.1. Concordance between molecular (PCR) and bacteriological methods

The frequency distribution of sputum samples positive or negative for specific bacterial species (including but not necessarily limited to *H. influenzae*, *M. catarrhalis*, *S. pneumoniae*, *S. aureus* and *P. aeruginosa*) obtained from PCR will be tabulated versus results obtained from culture at any visit (stable scheduled visits or AECOPD visits).

The concordance between culture and PCR, at any visit, will be evaluated using the Cohen's kappa (κ) statistic and 95% CI. Concordance will be interpreted as good (>0.79), substantial (0.60–0.79), moderate (0.40–0.59), fair (0.21–0.39) or no concordance (<0.21) (McHugh, 2012).

Proportion of patients with sputum samples positive for bacterial pathogens (including but not necessarily limited to *H. influenzae*, *M. catarrhalis*, *S. pneumoniae*, *S. aureus*, *P. aeruginosa*, *K. pneumoniae* and *A. baumannii*) by PCR will be computed, with 95% CIs, at each and any stable scheduled visit and at each and any AECOPD visit confirming acute exacerbation.

6.3.2. Proportion of potential bacterial/viral pathogens by country, GOLD grade and by AECOPD severity

Average proportion of patients with sputum samples positive for bacterial or viral pathogens overall and for specific species, will be computed, with 95% CIs, at any stable scheduled visit and at any AECOPD visit confirming acute exacerbation [mild, moderate, severe] by GOLD classification [GOLD 2, 3, 4].

Average proportion of patients with sputum samples positive for bacterial or viral pathogens overall and for specific species, will be computed, with 95% CIs, at any stable scheduled visit and at any AECOPD visit confirming acute exacerbation by country.

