11.2.4. Bacterial and viral PCR assays

- Multiplex real-time PCR (MPB1) assay will target *Haemophilus influenzae*, *Moraxella catarrhalis*, *Streptococcus pneumoniae* with quantitative results (copies/mL of sample).

For qualitative analyses, quantitative results must be converted in POS/NEG results. Only samples above the cut off will be considered as POSITIVE.

The positivity cut-off for each quantitative PCR assay will be defined at time of data release.

For quantitative analyses, only samples with load above the cut off will contribute to mean and SD computation.

CONFIDENTIAL

201112 (EPI-NTHI-001 BOD APA)
 Statistical Analysis Plan Amendment 2 Final

- Multiplex real-time PCR (MPB2) assay will target *Streptococcus pyogenes*, *Staphylococcus aureus*, *Pseudomonas aeruginosa* with qualitative results only (POS/NEG).
- Multiplex reverse transcription PCR assay will target different viral pathogens with qualitative results only (POS/NEG).
- HRV qPCR assay will target HRV with quantitative results (copies/mL).

For qualitative analyses, qualitative and quantitative results will be combined with the following algorithm:

Sample	Allplex HRV result	Allplex HEV result	HRV RT-qPCR	Final HRV result (variable to be derived)
1	POS	NEG	\geq LOD*	POS
2	POS	NEG	< LOD	POS
3	NEG	POS	\geq LOD	POS
4	NEG	POS	< LOD	NEG
5	NEG	NEG	Not tested	NEG
6	POS	NEG	0	POS
7	POS	POS	\geq LOD	POS

*The positivity cut-off for each quantitative PCR assay will be defined at time of data release. For quantitative analyses, only positive samples will contribute to mean and SD computation.

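### SAP 6.3.1 grades culture-PCR concordance by kappa band alone, and the band cannot tell extra PCR yield from contradiction between the two methods

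*SAP*

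**What the plan says.** Concordance between PCR and bacteriological methods is the first secondary objective listed in Protocol 2.2 and SAP 3.2.

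For this objective, SAP 6.3.1 plans:

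- A table, by bacterial species, in which results "obtained from PCR will be tabulated versus results obtained from culture at any visit".
- An agreement statistic: concordance "will be evaluated using the Cohen's kappa (κ) statistic and 95% CI".
- A reading rule: "Concordance will be interpreted as good (>0.79), substantial (0.60–0.79", then "moderate (0.40–0.59), fair (0.21–0.39) or no concordance (<0.21".

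The section names no positive, negative or overall percent agreement. It separately plans PCR-positive proportions with CIs, and SAP 6.2 plans culture-positive proportions with CIs.

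Three other places bear on the point:

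- Protocol 1.2 says that the few studies comparing the methods "demonstrated that PCR is more discriminatory at detecting typical airway bacteria". It gives no size for the difference.
- SAP 11.2.4 covers the quantitative assays (*H. influenzae*, *M. catarrhalis*, *S. pneumoniae*): "The positivity cut-off for each quantitative PCR assay will be defined at time of data release".
- SAP 7 limits all analyses to supportive or hypothesis-generating use.

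**The concern.** Kappa responds to three things at once: whether the methods agree on the same samples, how common the species is, and how far apart the two positive rates are. Here the positive rates are expected to differ. When PCR finds positives that culture misses, kappa falls, even if PCR never misses a positive culture.

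A low grade can thus mean that PCR adds detections, or that the methods disagree about which samples are positive. These are different answers to the objective, and the band gives the same word for both. Because the analysis is descriptive, that word is the stated conclusion. For three species it also depends on a PCR cut-off not yet fixed in the SAP, since the cut-off sets the PCR-positive rate.

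**Working it through.** **Inputs.** The bands come from SAP 6.3.1. The documents state no kappa, percent agreement or PCR/culture ratio for this analysis, so there is no figure of the plan to reproduce. Protocol Table 12, "Exact 95% confidence intervals of the percentage of occurrence of a specific bacterium from sputum collected during AECOPD", plans for 5% to 50%. Recomputing it by Clopper-Pearson reproduces all 24 intervals (for example N = 140, 5%: 2.0 to 10.0). For 240, 200, 160 and 50 enrolled, Protocol 9.2 says "one may expect around 180, 140, 120, 40 sputum samples, respectively"; 200 × 0.9 × 0.8 = 144 against the stated 140. The positive rates below are assumptions shown over a range.

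**Formulas.** Let c be the culture-positive share, p the PCR-positive share, po the observed agreement and pe the chance agreement.

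- kappa = (po − pe)/(1 − pe), with pe = cp + (1 − c)(1 − p).
- If PCR confirms every positive culture, po = 1 − (p − c) and kappa = 2c(1 − p)/[p(1 − c) + c(1 − p)].
- In that case positive agreement is 100% and negative agreement is (1 − p)/(1 − c).

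**Step 1: two different tables, one grade.**

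- Table A: c = 10%, p = 20%, full confirmation. kappa = 0.16/(0.18 + 0.08) = 0.615, 'substantial'. Positive agreement is 100% and negative agreement 0.80/0.90 = 88.9%. Discordant samples: 10% PCR+/culture−, 0% PCR−/culture+.
- Table B: c = p = 10%, same kappa. pe = 0.01 + 0.81 = 0.82, so po = 0.82 + 0.18 × 0.615 = 0.931. Discordant samples total 6.9%, about 3.5% each way. Both-positive samples are 10% − 3.5% = 6.5%, so PCR confirms about 65% of positive cultures.

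**Step 2: overall agreement fixed at 90%, full confirmation (p = c + 10 points).**

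| Culture-positive | PCR-positive | kappa | Grade |
|---|---|---|---|
| 2% | 12% | 0.26 | fair |
| 5% | 15% | 0.46 | moderate |
| 10% | 20% | 0.62 | substantial |
| 20% | 30% | 0.74 | substantial |
| 30% | 40% | 0.78 | substantial |
| 40% | 50% | 0.80 | good |

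The 2% row lies below the Table 12 range. Within that range the grade still runs from 'moderate' to 'good'.

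**Step 3: yield ratio varied at c = 10%, full confirmation.** A PCR/culture ratio of 1.0 gives kappa 1.00; 1.25 gives 0.88; 1.5 gives 0.77; 2 gives 0.62; 3 gives 0.41; 4 gives 0.29. 'Good' is lost above a ratio of about 1.5 at c = 5%, 1.45 at 10%, 1.4 at 20% and 1.3 at 30%. The grade falls to 'moderate' above about 2.2, 2.1, 1.9 and 1.7 respectively.

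**Step 4: ratio fixed at 2, full confirmation.** kappa is 0.64 at c = 5%, 0.62 at 10%, 0.55 at 20% and 0.44 at 30%. Here the commoner species grades lower, the reverse of Step 2.

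**Step 5: precision.** For c = 5%, p = 15% and n = 140, kappa is 0.46 with a large-sample 95% CI of 0.23 to 0.69, which touches three bands. This treats samples as independent and uses AECOPD samples only. The planned analysis also includes stable visits, so its interval would be narrower.

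**The case against.** The best defence is that the information is not lost. The full PCR-by-culture table is planned, so both discordant cells and both directions of agreement can be read from it. The separate PCR and culture proportions will show any higher PCR yield as higher yield. The objective is concordance, not PCR accuracy, so a PCR-positive, culture-negative sample is properly counted as non-concordant. Kappa is a conventional statistic, and no decision rests on its grade. All of this stands and limits the harm. It does not repair the reading rule, because the only interpretation written into the SAP ignores what the table would show.

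A second objection concerns the remedy. Take two equally good assays, each 90% sensitive and 99% specific with independent errors (assumed values). Kappa rises from 0.42 at 1% prevalence to 0.83 at 20%, and positive agreement of PCR against culture rises from 43% to 86%. Positive agreement therefore also varies with prevalence when both assays err. That is correct, and it is why it should be read beside the two positive rates. It still separates Table A from Table B (100% against about 65%), which kappa does not.

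A reader might also infer more than the documents support:

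- That unequal positive rates rule out 'good'. They do not: 10%/12.5% gives 0.88 and 40%/50% gives 0.80.
- That rare species will be graded down. With equal yield and full confirmation kappa is 1 at any prevalence, and Step 4 runs the other way.
- That a more sensitive PCR will generally be graded 'moderate'. At 5% to 10% culture positivity with full confirmation, a doubling is still 'substantial'.
- That species will be ranked by concordance. Neither document plans this.

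**Conclusion.** The point holds in a limited form. The kappa band mixes agreement with prevalence and with the difference in yield, and it cannot separate added PCR detections from contradiction between the methods. The clearest evidence is the shared kappa of about 0.62 for full confirmation and for about 65% confirmation. A fixed 90% agreement spanning 'fair' to 'good' shows the range.

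Which grade any species will receive cannot be predicted from the documents. It depends on culture positivity and the PCR/culture ratio, both assumed here, and for three species on a PCR cut-off set later. What is at risk is the wording of the conclusion for the first-listed secondary objective; the underlying data are not affected. The change is worth making because it is specific and nearly free.

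**What to change.** In SAP 6.3.1, report for each species, from the table already planned:

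- Positive and negative percent agreement of PCR against culture, each with a 95% CI, labelled as descriptive agreement so that culture is not taken as the truth.
- The culture-positive and PCR-positive rates side by side.
- The discordant samples split into PCR+/culture− and PCR−/culture+.

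Keep kappa with its 95% CI as a supporting figure. Replace the sentence that reads concordance from the bands with one that bases the conclusion on the items above, and state that percent agreement is to be read together with the two positive rates. The cost is a few more proportions per species and SAP wording.

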6.3.3. Sputum sample collection and quality

6.3.3.1. Sputum sample collection

The percentage of patients at each scheduled [stable] and exacerbation visit for whom a sputum sample is obtained will be computed overall and by the method the sample is obtained [i.e. spontaneous (at study visit or at patient's home), induced using 0.9% saline or induced using 3% saline]. The percentage of patients with induced sputum will be tabulated by GOLD grade at enrolment and by severity of the AECOPD. The proportion of sputum samples obtained at each confirmed stable or AECOPD visit [any, mild, moderate and severe] with or without induction and positive for specific bacterial\viral pathogens by bacteriological culture and bacterial\viral PCR will be computed.

The distribution of the number of sputum samples will be presented according to time (days) since the start of exacerbation. The distribution of the proportion of sputum sample positive for bacteria/virus given the number of days between the start of exacerbation and sample collection will be presented.

CONFIDENTIAL

201112 (EPI-NTHI-001 BOD APA)
 Statistical Analysis Plan Amendment 2 Final

The impact of previous antibiotic administration on bacterial results presence will be evaluated. The proportion of sputum samples obtained at each confirmed stable or AECOPD visit [any, mild, moderate and severe] with previous administration of antibiotics or not and positive for specific bacterial pathogens by bacteriological culture and PCR, respectively will be computed.

The impact of previous vaccination with a pneumococcal vaccine or an influenza vaccine (regardless of time) on *S. pneumoniae* and influenza virus will be evaluated. The proportion of sputum samples obtained at each confirmed stable or AECOPD visit with previous vaccination or not and positive for *S. pneumoniae*, by culture and PCR or influenza virus, by PCR, will be computed.

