6.3. Outline of study procedures

Table 4 presents the study procedures involved during scheduled [stable] visits.

Table 4 List of study procedures for scheduled visits

Epoch	Epoch 001			
	Type of contact	Screening Visit	Visit 1	Visit 2
Time point	Pre-Month 0	Month 0	Month 6	Month 12
Informed consent ^a	●			
Check inclusion/exclusion criteria ^a	●	○		
Record demographic data ^a	●			
Record medical history	●			
Record history of AE COPD within the previous year ^b	●			
Record intercurrent comorbidities ^c	○	●	●	●
Record history of pneumococcal and influenza vaccination	○	●	●	●
Smoking exposure history (ATS-DLD-78A questionnaire)/biomass exposure history (Biomass Exposure questionnaire)	○			
Smoking status	●	●	●	●
Physical examination including vital signs ^h	●	○	○	○
Urine Pregnancy Test	●	●	●	●
Measure/ record height and weight ^d	●			●
Pre- and post-bronchodilator spirometry ^e	●			●
Chest X-ray ^f	●			
Record subject's COPD status (stable, recovered or not recovered)		●	●	●
Record current medication		●	●	●
Record healthcare resource utilisation		●	●	●
Record additional treatments prescribed by primary and secondary care physicians		●	●	●
Train subject on use of electronic Diary Card and assign electronic Diary Card to the subject	○	○		
Return electronic Diary Card				○
Sputum sampling ^g	●	●	●	●

Epoch	Epoch 001			
Type of contact	Screening Visit	Visit 1	Visit 2	Visit 3
Time point	Pre-Month 0	Month 0	Month 6	Month 12
Blood samples for biomarkers		●		●
Record Adverse Events (AEs)* ^a	●	●	●	●
Record serious adverse events (SAEs) ^a	●	●	●	●
Screening conclusion	●			
Study conclusion				●
HRQOL questionnaires:				
CAT		0	0	0
SGRQ-C		0	0	0

● is used to indicate a study procedure that requires documentation in the individual eCRF.

0 is used to indicate a study procedure that does not require documentation in the individual eCRF.

^a For non-eligible subjects, only informed consent, inclusion/ exclusion criteria, demographic data and SAEs related to study participation that occurred after signing the informed consent pages need to be completed in the subject's eCRF. For other activities, 'not done' can be indicated.

^b Record both documented and self-reported, non-documented AECOPD. Subjects need documentation for at least 1 moderate or severe AECOPD within the previous year to be eligible for study participation.

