^j Only if clinically indicated to exclude another cause of worsening of symptoms (e.g. pneumonia). If a chest X-ray is clinically indicated but a chest X-ray/ CT scan has already been taken for that AECOPD as part of medical care before the study AECOPD visit takes places, the results of that chest X-ray/ CT scan can be used. All cases of pneumonia (including all signs and symptoms assessed to confirm pneumonia) should be documented in the eCRF.

^k Sputum can be collected spontaneously or can be induced, as per investigator judgement. Sputum sampling should only be done if, in the opinion of the investigator, it is safe for the subject.

^l Physical examination should be done only if necessary by the investigator or delegate.

^m AECOPD severity grading as indicated in Table 2.

ⁿ Non-serious AEs will be recorded in the eCRF and will not be entered into the safety database.

^{*} Refer to Table 10 for description of which AE/SAEs are collected in this study.

Table 6 presents the intervals between study visits.

Table 6 Intervals between study visits

Interval	Optimal length of interval	Allowed interval ¹
Screening Visit (pre-Month 0) → Visit 1	± 14 days	≤42 days before Visit 1
	Scheduled study visits	
Visit 1 (Month 0) → Visit 2 (Month 6)	182 days	175 - 203 days
Visit 2 (Month 6) → Visit 3 (Month 12)	182 days	175 - 203 days
AECOPD-driven study visit(s) and/ or phone contacts		
Onset AECOPD symptoms → AECOPD Visit	-	max 96 hours ²

¹ If an AECOPD occurs at the time one of the scheduled study visits is planned, the stable study visit should be rescheduled to a later date, when the subject is stable again and within the time window specified. In consultation with GSK, the concluding visit (Visit 3, Month 12) may however exceptionally be conducted outside of the allowed interval if necessary by the investigator.

² AECOPD visits will be scheduled as soon as possible after the onset of AECOPD symptoms as recorded in the electronic Diary Card or confirmed by the subject (maximum 96 hours after and, if applicable, preferably before starting treatment with antibiotics).

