6.4.2.3. Vaccination History

Record in the eCRF whether the subject received any influenza vaccination within the previous 12 months or has ever received any pneumococcal vaccination (including date of vaccination [as detailed as possible]).

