6.1. Analysis of demographics/baseline characteristics

The analysis of demographic/baseline characteristics will be performed on the FAS and on the all enrolled set only if the percentage of enrolled patients excluded from the FAS is 5% or more.

The following characteristics at enrolment will be summarized using descriptive statistics:

- Demographics such as age at enrolment, sex and race.
- Present and past medical history.
- History of AECOPD within the previous year (overall and by AECOPD severity).
- Pre- and post-bronchodilator spirometry results.
- COPD status using the GOLD grade.
- Smoking/biomass exposure history status.
- Selected results and several risk factors from the ATS-DLD-78-A questionnaire.
- Physical examination/vital signs results such as height, weight, BMI, heart rate, respiratory rate, systolic and diastolic blood pressure.
- Chest X-rays results.
- Intercurrent comorbidities (reported at visit 1)
- History of pneumococcal and influenza vaccination (reported at visit 1)

CONFIDENTIAL

201112 (EPI-NTHI-001 BOD APA)
 Statistical Analysis Plan Amendment 2 Final

The following descriptive statistics will be adopted:

- The frequency and the percentage of each category will be reported for categorical variable.
- Number of non-missing observations, mean, median, standard deviation, minimum and maximum will be provided for quantitative variable.

All tables will be also generated by country.

Demographics and baseline characteristics will be also summarized for study sample for interim analysis.

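### SAP 6.3.3.1 sets no time limit on influenza vaccination, although the protocol records it only for the previous 12 months, so a dose up to about 25 months old can class a late sample as vaccinated

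*SAP*

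**What the plan says.** SAP 6.3.3.1 opens this analysis with: "The impact of previous vaccination with a pneumococcal vaccine or an influenza vaccine (regardless of time) on" two targets, namely *S. pneumoniae* and influenza virus. The comparison follows: "The proportion of sputum samples obtained at each confirmed stable or AECOPD visit with previous vaccination or not and positive for" either *S. pneumoniae* (culture and PCR) or influenza virus (PCR). One classification serves both vaccines, and no season or interval stratum is given.

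The protocol separates the vaccines. Section 6.4.2.3 instructs sites: "Record in the eCRF whether the subject received any influenza vaccination within the previous 12 months or has ever received any pneumococcal vaccination", with the date requested ("including date of vaccination [as detailed as possible"). I take the date request to cover both vaccines. In Table 4 (section 6.3) the row "Record history of pneumococcal and influenza vaccination" requires an eCRF entry at Visits 1, 2 and 3, but not at Screening. Table 5, for AECOPD visits, has no vaccination row.

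SAP 6.1 lists "History of pneumococcal and influenza vaccination (reported at visit 1") among the baseline characteristics. Section 6.3.3.1 does not say whether a sample's status comes from that baseline record, from the answer at the nearest scheduled visit, or from any record up to that time.

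**The concern.** Influenza vaccine is seasonal, and the protocol's own question reflects this by asking about the last 12 months only. The SAP drops that distinction, although it treats season as relevant elsewhere: section 6.3.5.1 reports exacerbations containing influenza A and B by month, and section 6.4.4 uses a high and a low season.

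Two things follow from the literal rule. First, a late sample can be classed as vaccinated on a dose given one or two seasons earlier. If such doses protect less, the vaccinated group's influenza positivity moves toward that of the unvaccinated group. Second, the rule does not fit the data collected. The item cannot identify a dose older than 12 months at Visit 1, yet the rule lets recorded doses age without limit afterwards. At stake is the interpretability of one planned secondary tabulation.

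**Working it through.** **Plan's own figure.** The documents give no number for this analysis: no vaccine coverage, revaccination rate, effectiveness or influenza positivity. There is nothing to reproduce.

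**Oldest dose that counts.** Inputs: a 12-month look-back at Visit 1, taken as 365 days (Protocol 6.4.2.3), and visit intervals of 182 days optimal and 203 days maximum (Protocol Table 6). Age of dose at sample = 365 + days from Visit 1 to the sample; months = days / 30.44.

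| Sample at | Optimal schedule | Latest within window |
|---|---|---|
| Visit 1 | 365 days = 12.0 months | same |
| Visit 2 | 365 + 182 = 547 days = 18.0 months | 365 + 203 = 568 days = 18.7 months |
| Visit 3 | 365 + 364 = 729 days = 24.0 months | 365 + 406 = 771 days = 25.3 months |

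The 771 days is not a hard cap, because the concluding visit "may however exceptionally be conducted outside of the allowed interval if necessary by the investigator".

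**What the recorded data can support.** Take a sample t days after Visit 1.
- Any-time status needs the whole history before Visit 1, which is not collected for influenza. A dose 13 months before Visit 1 is missed, while one 12 months before Visit 1 is still counted at Visit 3.
- Twelve-month status needs only doses between day t − 365 and day t. As t is at least 0, this never reaches back beyond 365 days before Visit 1, which the Visit 1 question covers. Later doses are covered at Visits 2 and 3, because each interval (at most 203 days) is shorter than the look-back. The record is therefore complete for a patient who attends the next scheduled visit.

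**Share of doses older than 12 months.** Assume that last doses are spread evenly over the 12 months before Visit 1 and none is repeated. The share is then 0 at Visit 1, 182/365 = 50% at Visit 2 and 364/365, or about 100%, at Visit 3. Revaccination reduces these in proportion and could bring them close to zero.

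**Effect on the contrast (assumptions only).** Let VE be the relative reduction in positivity from a dose within 12 months, s the share of vaccinated samples with only an older dose, and VE_old the reduction from that older dose. Observed reduction = VE × (1 − s) + VE_old × s.

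| VE | s | VE_old = 0 | VE_old = VE/2 |
|---|---|---|---|
| 40% | 0.10 | 36% | 38% |
| 40% | 0.25 | 30% | 35% |
| 40% | 0.50 | 20% | 30% |
| 60% | 0.10 | 54% | 57% |
| 60% | 0.25 | 45% | 52.5% |
| 60% | 0.50 | 30% | 45% |

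For example, 0.40 × 0.75 + 0 = 0.30, and 0.40 × 0.75 + 0.20 × 0.25 = 0.35.

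**Precision, for context.** Protocol 9.2 expects around 140 AECOPD samples from 200 patients (200 × 0.90 × 1 × 0.80 = 144). Split them evenly by vaccination and assume 10% positivity without vaccination, VE = 40% and VE_old = 0. The difference is 10% − 6% = 4.0 points undiluted, and 10% − 7% = 3.0 points at s = 0.25. Power is about 14% and 9%.

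**The case against.** The strongest reply is that the SAP does not name the record that sets a sample's status. If the answer given at each visit is used, an unrepeated dose from before Visit 1 reads as no at the latest Visit 3 date, and the 25-month case disappears. That is a possible reading, but it sits badly with a rule that says time is ignored. Either way the text needs correcting.

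Several further points stand. Nothing in the documents establishes waning or missed revaccination. The 25 months applies only near Visit 3; at Visit 1 the maximum is 12 months. No study objective mentions vaccination, Protocol 9.6 does not list this comparison, and SAP section 7 makes all analyses descriptive. The comparison is imprecise and unadjusted, so country, season and the reasons for being vaccinated may matter more than dilution. The rule is also explicit and appears in all three SAP versions, so it is transparent. Transparency does not make it fit the data collected.

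A 12-month rule has its own weaknesses. If older doses keep some effect, moving them to the comparison group contaminates that group. It also depends more on dates. Under SAP 11.3.1 a dose known only by year is set to 30 June. A true dose on 15 October 2017 would become 30 June 2017; for a sample on 15 August 2018 the interval changes from 304 to 411 days, and the status flips. Doses between scheduled visits are known only at the next one and may be lost on withdrawal. These are reasons to keep the any-time version alongside, not to keep it alone.

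**Conclusion.** The mismatch is real. SAP 6.3.3.1 ignores time since influenza vaccination, whereas the protocol collects it on a 12-month look-back. Taken literally, the rule counts doses up to 771 days old within the visit windows and misses a dose given 13 months before Visit 1. This part rests on the text and on visit arithmetic alone.

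The consequence is conditional. If protection falls with time or season and some patients are not revaccinated, the comparison is likely to be pulled toward no difference. The size is unknown from the documents and could be near zero with yearly revaccination; the percentages above illustrate assumed inputs.

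A reader might infer three stronger things that the documents do not support:
- That the vaccine contrast is certainly diluted. This needs waning and revaccination figures that neither document gives.
- That the primary endpoint is compromised because influenza virus is one of its species. The proportions in SAP 6.2 do not use vaccination status and are unchanged.
- That the plan will conclude there is no vaccine effect. Section 6.3.3.1 only computes proportions; it sets no test or decision rule.

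Sample size is not affected. This is a cheap, worthwhile correction to one descriptive analysis.

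**What to change.** Amend SAP 6.3.3.1 as follows.
- **Pneumococcal vaccine:** keep the ever rule, restricted to doses before the sample.
- **Influenza vaccine:** class a sample as vaccinated if the most recent dose precedes the sample date and falls within the previous 12 months. Name the source as the dates recorded at Visits 1 to 3, and for AECOPD samples include doses first reported at the next scheduled visit.
- **Sensitivity:** tabulate the any-time influenza classification next to the 12-month one.
- **Partial dates:** show samples whose status depends on the 30 June imputation separately, or as unknown.
- **Minimum interval from dose to sample:** the documents give none. If the sponsor wants one, it should choose and justify it.

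The cost is SAP wording, one date comparison and an extra tabulation, with no new data collection if the eCRF holds influenza dates as Protocol 6.4.2.3 appears to require. The downside is small: some samples will have uncertain status because of partial dates, or because a patient withdrew before the next scheduled visit.
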